PROMIS-29. The Patient-Reported Outcomes Measurement System 29-item Health Profile (PROMIS-29) has good evidence of reliability and responsiveness, and is suitable for telephone administration. PROMIS has published its results in 20000+ adults, many with MCC, and has been recommended by the Working Group on Health Outcomes for Older Persons with Multiple Chronic Conditions, an expert panel convened by the National Institute of Aging in collaboration with Agency for Healthcare Research and Quality.¹⁶ The tool has also undergone extensive valuation work enabling translating PROMIS-29 responses into quality-adjusted life-years.³³

Physical Activity Scale for the Elderly (PASE). The PASE is a self-report, 12-item scale that measures occupational, household, and leisure activity during a one-week period.³⁴ This scale was developed for use among older adults and has been validated for use via telephone.

Medical Outcomes Study: Short Form Social Support Survey Instrument. This 8-item measure reflects how often a person looks to others for companionship, assistance, or other types of support, and is well-validated.³⁵

Depression and anxiety. It is important to note that eligibility for the current study depends on the results of a cognitive screener administered on one occasion and this does not constitute a formal diagnosis of any cognitive disorder. Nevertheless, we expect that some participants will be referred for further testing and may receive a diagnosis in a clinical setting. There have been no studies reporting harm related to receiving a diagnosis of CI; however, some groups have raised concerns about this possibility. Thus we will measure symptoms of depression (Patient Health Questionnaire [PHQ]-9) and anxiety (General Anxiety Scale [GAD]-7) at baseline and the 14 week follow-up call. The PHQ-9 is a nine item depression scale that is well validated and documented in a variety of populations including a geriatric populations and primary care settings.³⁶ The GAD-7 is a 7-item anxiety scale with good reliability, as well as criterion, construct, factorial, and procedural validity.³⁷ We will utilize a safety protocol to address suicide risk identified during the administration of study measures (Appendix).

Other Measures. We will collect information on patient socio-demographics, chronic medical conditions, self-rated health, health literacy, and sleep questions. We will review patient medical records to determine actions taken by the PCP as a result of the TICS-m score progress note (e.g. Geriatrics, Neurology referrals, Neuropsychology testing, scheduling a follow-up visit, etc.) and new diagnoses of CI or dementia.

D.7. Analyses

D.7.a. Aim 1: Examine the *feasibility* and *acceptability* of a 12-week care management program for medically complex Veterans with CI, delivered via telephone or through video visits. Feasibility will be examined by calculating overall rates of eligibility and enrollment, as well as rates of attrition, adherence to nurse calls or video visits, and interview completion. Clinical and personal characteristics associated with enrollment and study completion will be explored as well via contingency tables and regression analyses. Acceptability will be assessed using in-depth interviews with study participants (Veterans and Care Partners), primary care providers, and study staff (Section D.6.b.). We will conduct a formative evaluation of the intervention in order to elicit information about ways to enhance acceptability and effectiveness of the intervention in anticipation of testing it in a larger study.³⁸ Collecting qualitative data from relevant stakeholders including study participants, PCPs and study staff, will provide additional rich context for interpreting other quantitative study results.³⁹ Tasks and methods for each evaluation stage are described in the Appendix.

D.7.b. Aim 2: Assess the *usability* and *perceived value* of video-enhanced care management, compared to telephone-based, among older Veterans with medical complexity and CI. We will administer the SUS at the 14-week outcome call to participants randomized to Arm 2 (video-enhanced.), care partners, and clinical staff. If any participants choose to withdraw from this Arm, we will administer this measure prior to withdrawal. We will examine overall sample mean, median, and distributions of scores according to established thresholds (e.g. >70 = excellent usability among those aged ≥65 years). Additionally, we will look at responses to individual items to see if certain items are more frequently endorsed (e.g. technical support item) to make refinements prior to a larger RCT. We will calculate means (or medians, as appropriate) and distributions of hospitalizations, ED visits, and patient-reported outcomes (PROMIS 29, PASE, MOS Social Support, PHQ-9, GAD-7) across time points, as well as changes between baseline and 14-week follow-up, as appropriate. Because of the small sample size, we will not conduct statistical testing. However, our descriptive analyses will allow us to evaluate whether there are clinically relevant differences in mean study outcomes between the two Arms (video-enhanced vs. telephone-based). Perceived value associated with each delivery method will be explored through questionnaires and in-depth interviews with study participants and study staff.

D.7.c. Sample size considerations. This is an exploratory pilot study that is not intended to test efficacy. While the sample size chosen must reflect the pragmatics of recruitment during a short enrollment period, we will have adequate sample size to provide meaningful confidence intervals for our estimates of feasibility, and comparisons between video and telephone delivery methods, and will have sufficient diversity of input on the intervention to plan refinements, if needed, prior to testing it in a larger RCT.

D.8. Dissemination and Implementation Plan

The results of this pilot study will provide essential information about the feasibility, acceptability, usability, and perceived value of a care management program for medically complex Veterans with CI, delivered via telephone or through video visits on iPads. By using these preliminary data to refine study methods and optimize the intervention protocol prior to conducting a large RCT, we will enhance the efficiency and overall value of the subsequent trial. Specifically this pilot study addresses the important question of whether providing care management via video visits is feasible in this population, and if so, whether it offers added benefits, compared to telephone. To examine video visits, we will use the Pexip Infinity application which is currently approved and in preliminary clinical use in VHA, making rapid implementation highly feasible, if proven effective.

D.9. Project Management Plan

D.9.a. Summary of Research Team Experience. The research team is comprised of investigators from the HSR&D COIN for Health Services Research in Primary Care; the Geriatrics, Research, Education and Clinical Center (GRECC) at the Durham VA, the Duke University Center for the Study of Human Aging and Development and Alzheimer's Disease Research Center. We have assembled a multidisciplinary study team with a track record of productive collaboration, as well as relevant experience with all the methodology, data sources and analytic techniques described in the current proposal.

D.9.b. Timeline. We propose a **1 year study**. As illustrated below, we expect to begin enrollment in month 4 and complete data collection by month 10. The remainder of the study period will be dedicated to analysis of the data, dissemination of study results, and preparation of an IIR to test the intervention in an RCT.

	Month											
	1	2	3	4	5	6	7	8	9	10	11	12
Project Start Up												
Finalize IRB	X	X										
Develop study database and procedures	X	X	X	X								
Intervention Implementation												
Enroll patients				X	X	X	X					
Intervention and outcome assessments					X	X	X	X	X	X		
Data Analysis												
Planning for data analysis									X	X	X	X
Data analysis and reporting/ Prepare IIR											X	X

D.10. Data Management

The Durham HSR&D CoE adheres to VA policy and Durham VAMC IRB requirements, but has also developed additional Standard Operating Procedures for data security which have been designed to ensure continued confidentiality, integrity, and availability of research data. These procedures, which protect both paper and computer based records, have been used successfully in many studies, and will be followed for the proposed study.

With respect to all data, these procedures mandate the following to ensure confidentiality and safe handling of all data: (1) Access to all participant data and information will be restricted to authorized personnel; (2) Participants will not be identified by name in any reports or publications, nor will data be presented in such a way that the identity of individual participants can be inferred; (3) Each participant will be assigned an anonymous study ID which will be used on all study forms; and (4) All study personnel will maintain certification with the Durham VAMC IRB that they have completed training in research ethics and confidentiality.

With respect to paper based records, these procedures mandate the following: (1) All study records that contain participant information will be kept in secured locked areas when not in use; and (2) In addition, such materials, when in use, will be kept safe from public scrutiny. With respect to computer based records, the following practices are followed: (1) All research data are stored on VA-administered servers which are physically secured in a Durham VAMC server room; (2) Individual computer accounts, password protected, are issued to staff members; and (3) Access to computer data is granted by OI&T personnel after confirming appropriate documentation through the IRB, per CoE policies. Utilization data will be downloaded directly from national files to the Durham HSR&D CoE servers. Of study personnel, only the study Statisticians and Economist will have access to these data, which will not be moved from this secured environment.

The key linking the study ID numbers to the patients identifying information will be stored in a password protected electronic database and maintained on a password protected VA server, with access only available to approved study staff and investigators. The name and phone number of family members identified by the subject will also be recorded here.

D.10. a. Lists of Data Reviewed and/or Collected for Screening/Recruitment and Conduction of Study:

The Personal Health Information that will be used or shared for this study includes:

Identifier(s)	Source(s) of Health Information
 Names	 Medical history & physical exam information
 All geographic subdivisions smaller than a State, including street address, city, county, precinct, and zip code	 Photographs, videotapes, audiotapes, or digital or other images
 All elements of dates (except year) for dates directly related to an individual, including birth date, admission date, discharge date, visit or treatment dates, etc.; and all ages over 89	 Biologic specimens (e.g., blood, tissue, urine, saliva)
 Telephone numbers	 Progress notes
 Fax numbers	 Diagnostic / Laboratory test results
 Electronic mail addresses	 Operative reports
 Social Security Numbers	 Imaging (x-ray, CT, MRI, etc.)
 Medical record numbers	 Discharge summaries
 Health plan beneficiary numbers	 Survey / Questionnaire responses
 Account numbers	 Billing records
 Certificate and/or license numbers	 HIV testing or infection records
 Vehicle identifiers and serial numbers, including license plate numbers	 Sickle cell anemia information
 Device identifiers and serial numbers	 Alcoholism or alcohol use information
 Web Universal Resource Locators (URLs)	 Drug abuse information
 Internet Protocol (IP) address numbers	 Mental health (not psychotherapy) notes
 Biometric identifiers, including finger & voice prints	 Psychological test results
 Full-face photographic images and any comparable images	 Genetic testing
 Any other unique identifying number, characteristic, or code, describe: Study ID Numbers	 Other, describe:

All non-Veterans enrolled in this study will receive the VA Notice of Privacy Practices (NOPP) and are requested to sign the acknowledgment form. The signed acknowledgment form will be maintained with the research records.

1. Data and/or Specimen Acquisition:

Data for this study will be collected through:

- Prospective data and/or specimen collection obtained from participants. Please see section D.3 – D.6. for a description of the data collection process.
- Retrospective data collection and/or specimens obtained from medical chart review/data access. Describe how data will be obtained (e.g., fileman, CDW, etc.): Please see section D.3 – D.6. for a description of CDW data and medical chart review used to screen for eligibility, Utilization data will be downloaded directly from national files to the Durham HSR&D CoE servers..

Retrospective data collection and/or specimens obtained from an IRB-approved data and/or specimen repository. Indicate the repository source including name, VA location, and IRB number:

2. Level of Data:

The following level(s) of data will be acquired/maintained for this study (*check all that apply*):

- Identified (e.g., names, addresses or other identifiers included)
 Coded (direct and/or all identifiers removed, but study code/ID included)
 De-Identified (all HIPAA 18 and study ID/code removed):
 Verified Statistically
OR
 Verified by Absence or Removal of HIPAA 18 and study ID
 Limited Data Set
 Other: Describe:

3. Location of Data and/or Specimens, and Data Retention Plan:

A. Data and/or Specimen Location: VHADURSQLH5.v06.med.va.gov (SQL database server) and \\vhadurhsrdfile1.v06.med.va.gov\\$\projects\SECSI(shared document folder)

Data will be also be placed at the VA Informatics and Computing Interface (VINCI; <http://vaww.vinci.med.va.gov/vincicentral/VINCIWorkspace.aspx>).

B. Data Retention Plan

Current VA regulations regarding research records retention does not allow for the discarding of records. After the close of the protocol if VA records and retention regulations allow for the destruction of paper research records, files will be shredded in accordance with VA records control requirements and information in electronic format will be deleted or purged from data files in accordance with VA records control requirements.

Other data retention plan, describe:

4. Data Access and Data Recipients:

Only VA research study personnel will have access to identifiers and coded data, in accordance with VA policy, on the requirements of Federal privacy and information laws and regulations, VA regulations and policies, and VHA policy. This will only be done behind VA firewalls. All study personnel who are VA employees working within the VA system have fulfilled all required HIPAA and other VA security and privacy policy training requirements and have agreed to follow guidelines pertaining to the protection of patient data. All research staff sign VA Rules of Behavior, and all study staff are up-to-date with VHA Privacy Policy Training and the VA Office of Cyber and Information Security Awareness Training Course. The data security and privacy procedures summarized in that course include logging off or locking the computer when walking away from it; no sharing of access codes, verify codes or passwords; not allowing anyone else to use the computer under one's password; and disposing of sensitive information using VA-approved methods (e.g., shredder bins). Access to study data will be removed for all study personnel when they are no longer part of the research team.

5. Data and/or Specimen Transportation and/or Transmission for all data and/or specimens involved in the study:

Data will not be transported or transmitted outside of the VA.

- I. Data and/or specimens will not be transported or transmitted outside of Durham VAMC environment.
- II. Data and/or specimens will be transmitted to other VA sites using the following method(s):

A. Data

- Data are de-identified and thus will be sent via unencrypted e-mail or unencrypted disk (encryption is optional).
- Data are coded or contain identifiers and thus will be sent <chosed method of transfer such as: PKI or RMS encrypted e-mail, FIPS 140-2 encrypted disk (with VA-authorized carrier and tracking), or FIPS 140-2 encrypted external drive (with VA-authorized carrier and tracking). You may identify a primary and secondary method>.
- Other, describe:

B. Specimens

- Specimens are de-identified and thus will be sent via standard carrier (tracking is optional).
- Specimens are coded or contain identifiers and thus will be sent via VA-authorized carrier with tracking.
- Other, describe:

III. Data and/or specimens will be transported to non-VA/VHA sites (e.g., academic affiliates, laboratories, etc.) using the following method(s):

A. Data

- Data are de-identified and thus will be sent via unencrypted e-mail or unencrypted CD.
- Data are coded or contain identifiers and thus will be sent via <chosed method of transfer such as FIPS 140-2 encrypted CD or FIPS 140-2 encrypted hard drive/flash drive> using VA—approved carrier with tracking.
- Data are coded or identified and will be uploaded to sponsor website using electronic case report form (eCRF)
- Other, describe:

B. Specimens

- Specimens are de-identified and thus will be sent via standard carrier (tracking is optional) or will be hand-delivered by research study personnel. Specify method of delivery:
- Specimens are coded and thus will be sent via VA-approved carrier with tracking or will be hand-delivered by research study personnel. Specify method of delivery:

In accordance with the HIPAA and the Privacy Act, for any coded or identifiable data or specimens released from the Durham VAMC (with the exception of Limited Data Sets), an Accounting of Disclosure (AOD) will be maintained (e.g., in a database or spreadsheet) that includes the participant’s name, date of the disclosure, description of the nature of the Individually Identifiable Information (III) disclosed, purpose of each disclosure, and the name and address of the person/agency to whom the disclosure was made.

6. Risk Mitigation Strategies:

- Data are fully de-identified (stripped of HIPAA 18 and study ID/code) before being shared outside of Durham VAMC.
- Specimens are fully de-identified (stripped of HIPAA 18 and study ID/code before being shared outside of Durham VAMC.
- Direct identifiers will be maintained separately from data and or specimens by using a code to “identify” subjects. In a separate database (i.e., a “linking” or “cross-walk” database) this code will be linked to identifying subject information.

The patients’ right of privacy and the confidentiality of the protected health information will be guarded through strict controls and safeguards for access of the data to members of the research team. All study data will be stored on VA servers maintained by OI&T staff to comply with VA information security requirements. This includes study tracking and Datstat Ilume survey databases on server VHADURSQLH5.v06.med.va.gov, and project shared document folder \\vhadurhsrdfile1.v06.med.va.gov\projects\SECSI (usually mapped on users’ systems as P:\SECSI). Access to database and file systems is granted to research personnel via membership in Active Directory security groups created by OI&T; limited to individuals on the IRB staff listing. Members are removed from the security group when they no longer require access to study data. Data will not be stored on desktop or laptop computer hard-drives. Only VA approved staff will have access to the data file for data analysis. The PI will have ultimate responsibility of access to the data. Furthermore, data will be kept in accordance with VA records control schedule.

- Other, specify:

7. Suspected Loss of VA Information:

Should any incident such as theft or loss of data, unauthorized access of sensitive data or non-compliance with security controls occur it will be immediately reported according to VA policy. All incidents regarding information security/privacy incidents will be reported to the ISO and PO within 1 hour of acknowledgement of issue and done so using the VHADUR Research Events Report e-mail group ([contact]).

8. Reporting of Results:

- Reporting of results, such as in scientific papers and presentations, will never identify individual subjects. Data will be presented in aggregate and individual-level data will not be published.
- Other results reporting plan, describe:

Data Analysis and Statistical Considerations

Due to the small sample size, statistical analysis will not be performed on the sample.

References

Provide references, if applicable.

N/a

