D.2.c. Cognitive Screening Procedures. The TICS-m (9-11 min administration time) is a 50-point global cognitive screening tool that has been well-validated for use in multiple populations and was specifically designed for use over the telephone (i.e. no visually mediated items). TICS-m scores in elderly populations have been shown to be normally distributed and without evidence of a ceiling effect which limits the ability of other instruments to detect early CI.²⁵ TICS-m has been used as a reference standard for telephone-based detection of cognitive impairment.^{26,23} Participants with score between 20 and 31 (education-adjusted) will be eligible for the study, because scores in this range have been shown to correlate with cognitive impairment in the mild range²³ and to differentiate normal from impaired individuals when adjustment for education level is included. The small number of patients who scored in the 30-31 range and did not initially meet criteria for eligibility in the first months of study enrollment (original TICS criteria range = 20-29) will be re-contacted by study staff and offered participation. The VHA "Screening for Cognitive Impairment" directive does not recommend screening for cognitive impairment in asymptomatic older adults. The directive also states clinicians should be alert to early signs or symptoms of cognitive impairment and evaluate as appropriate. Therefore, at each nurse encounter, participants will have a note entered into the electronic health record (CPRS) notifying the patient's primary care team of any relevant clinical issues. If symptoms of cognitive impairment are noted by either the nurse manager or care partner an alert notifying the team of the noted symptoms will also be included in the CPRS progress note.

D.2.d. Exclusion criteria (Veteran). Patients will be excluded if they meet **any** of the following:

1. CI or dementia (identified via ICD diagnosis codes or PCP note in previous 2 years)
2. Enrolled in or have an active consult for a special population PACT (e.g. GeriPACT, Home Based Primary Care, Mental Health, Post-Deployment, etc.)
3. Are enrolled in a study that prohibits participation in another study
4. Serious mental illness defined as diagnosis of psychosis of any type, schizophrenia, bipolar disorder, psychiatric hospitalization in the previous year or current high-risk suicide flag in their CPRS medical record
5. Are currently hospitalized or incapacitated for any reason

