6. Active substance abuse, documented in the medical record within the previous year
7. Eligible for hospice, palliative care, or prognosis of less than 6 months to live
8. Lack decision-making capacity, documented in the medical record
9. Referred to institutional care or residing in nursing home
10. Unable to communicate on the telephone, or no telephone access for duration of study
11. Care Partner fails six-item screener or has no access to phone, and no other Care Partner available

[figure not shown]
At the clinical discretion of the study physician (PI), subjects may be enrolled in the study with an exclusion criteria if the clinical criteria (#1, 4, 7) is determined not to affect eligibility (for example, a previous dementia diagnosis in a patient whose clinical record notes do not indicate evidence of dementia).

D.2.e. Care Partners. The Veteran participant will identify their Care Partner of choice. Care Partners must be aged 18 or older, able and willing to provide informed consent for study participation (must score 5 or higher on a brief and reliable 6-item cognitive screen),²⁶ and able to communicate by telephone. In order to serve as the Veteran's Care Partner, an individual must be willing to join the Veteran for telephone or video calls and participate in outcome assessment calls. We propose to enroll dyads for three key reasons. First, the study focuses on older Veterans with CI; the participation of a partner can help the Veterans to understand and implement care recommendations, as well as access the technology required for video visits. Second, in our pilot studies, many Veterans expressed to us that their usual and preferred manner of receiving health information is through a spouse or adult child.²¹ Third, this is consistent with the growing literature about the

important role of companions in medical care, and expert recommendations that care be better integrated with family and caregivers.^{16,27}

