D.2.f. Recruitment Pool. The number of Veterans who would have been eligible for this study in March, 2015 based on age, CAN score ≥ 90 , and no pre-existing diagnosis of dementia is listed in Figure 4. In our pilot work, we examined the prevalence of other eligibility criteria and found that 1.3% did not have a valid telephone number, 1.7% were nursing home residents, and 1.9% were unable to talk on the telephone. Therefore, taking additional exclusions into account and anticipating 34-40% will score between 20 and 29 on the TICS-m, we project that 475-600 Veterans will meet all study eligibility criteria. It is anticipated that because the population of patients selected for this study will have at least a CAN score > 75 , they may seek additional medical care for events related to their diseases (and care may involve hospitalizations). They may also experience seasonal health issues such as flu or allergies. It is also anticipated that during study participation, they may seek medical assistance to recover from accidents or planned surgical procedures.

D.3. Enrollment Procedures. Using an automated data pull, study staff will first identify the patients who meet criteria for age and CAN score and apply exclusion criteria based on clinic stop and diagnosis codes available in CDW. Study staff will then conduct a brief medical record review to check for exclusions that are not readily available in CDW (e.g. residential status). During the medical record review study staff will determine if the patient has “decision-making capacity” by searching the medical record notes section using the key term “capacity”. The patient will be considered initially eligible if study staff finds that the patient has decision-making notated in the medical record. The patient will not be initially eligible if the term or similar term “lack of decision-making capacity” is found in the record. If term “capacity” is not found, study staff will assume decision-making capacity is intact. Of those eligible, we will mail introductory recruitment letters signed by the PI (see Sample Letter; Appendix). Patients will be provided a toll-free number to

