contact if they do not wish to be contacted further. Starting about one week after mailing recruitment letters, a member of the study staff will call patients to ascertain eligibility and obtain informed consent from the Veteran participant and Care Partner. During the phone screen process, study staff may use their discretion with the input of the Care partners to further determine whether the patient’s decision-making capacity is intact. For the Care Partner, the Six Item Screener (SIS), a cognitive assessment instrument, will be administered by trained study staff prior to Care Partner consent. If there is any question as to whether or not a potential adult subject has decision-making capacity, study staff will consult with a qualified practitioner (i.e., the study physician or study RN) about the individual’s decision-making capacity before proceeding with the informed consent process. Because the screening and enrollment is entirely telephone based, we will seek a waiver of documentation of informed consent, as approved by the Durham VAMC IRB in our ongoing studies using similar recruitment methods.

Figure 4. Study Recruitment Pool

D.3.g. Rationale for Enrollment and Screening over the Telephone. We have opted not to enroll Veterans at a primary care visit or other in-person visit for a number of reasons. First a telephone-based strategy expands the reach of the intervention by allowing enrollment from multiple community-based outpatient care clinics and not just the main hospital clinic. Most importantly this strategy mimics more closely how this intervention would be implemented if effective. We will track number of attempts to contact, and examine differences between patients who enrolled or refused and those we were unable to contact to inform future implementation efforts.

D.3.h. Randomization Procedure. Once patients and Care Partners have provided verbal consent and completed the baseline measurement battery, study staff will randomize the Veteran to Telephone-Based Care Management (Section D.4) or Video-Enhanced Care Management (Section D.5). Randomization assignments will be performed by the study statistician and the entire study randomization will be done before patient enrollment begins. We will stratify randomization based on whether or not patients are ‘experienced with relevant technology’. Participants will be considered ‘experienced with relevant technology’ if they indicate use

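### The chart search for exclusion 8 uses one word, 'capacity', and treats no hit as intact, so charts recording incapacity in other words clear the initial chart step

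*Combined protocol and SAP*

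**What the plan says.** D.2.d lists the Veteran exclusions under a header that makes any single one sufficient: "Patients will be excluded if they meet any of the following". Item 8 is a record-based criterion: "Lack decision-making capacity, documented in the medical record". It carries no time limit. Items 1 and 6 do (two years and one year), as does the psychiatric-hospitalization part of item 4 (one year). Item 5 is separate: "Are currently hospitalized or incapacitated for any reason".

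D.3 turns item 8 into a chart procedure. Staff work by "searching the medical record notes section using the key term “capacity", and three rules follow:

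- First, for a chart with a positive note: "The patient will be considered initially eligible if study staff finds that the patient has decision-making notated in the medical record" (read here as capacity being noted as present)
- Second, for a chart with a negative note: "The patient will not be initially eligible if the term or similar term “lack of decision-making capacity” is found in the record"
- Third, the default for a chart where the search returns nothing: "If term “capacity” is not found, study staff will assume decision-making capacity is intact"

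At the later telephone screen, "study staff may use their discretion with the input of the Care partners to further determine whether the patient’s decision-making capacity is intact". D.3 then requires staff to consult the study physician or study RN before consent whenever there is any question about a potential participant's capacity.

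**The concern.** Item 8 asks what the record documents. The procedure asks whether one word appears in it. Where a chart documents incapacity in different words, the third rule does not leave the matter open. It assigns intact capacity, the opposite of what the chart says. So this is a stated rule with a wrong output, not merely an unspecified detail.

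Two things are at stake. The first is participant protection: Veterans are recruited because they screen positive for cognitive impairment, enrollment is entirely by telephone, and the plan seeks to waive written documentation of consent. The second is reproducibility: the eligibility rate is an Aim 1 feasibility measure (D.7.a), and two staff members applying D.3 to the same chart could classify it differently.

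**Working it through.** The plan gives no figure on this point, so the check is of the rule's logic.

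**Step 1. Which wordings does the key term find?** The test is whether the literal string 'capacity' occurs in the phrase. The phrases are illustrative, except that 'incapacitated' is the protocol's own word in item 5.

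| Chart wording | Contains 'capacity'? | D.3 outcome |
|---|---|---|
| lack of decision-making capacity | yes | not initially eligible |
| lacks capacity; incapacity | yes | not initially eligible, as a similar term |
| has decision-making capacity | yes | initially eligible |
| incapacitated | no | assumed intact |
| incompetent | no | assumed intact |
| not competent | no | assumed intact |
| guardian appointed | no | assumed intact |
| unable to make own decisions | no | assumed intact |
| lung capacity | yes | no rule applies |

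**Step 2. Does the allowance for a similar term repair this?** There are two readings. If similar terms are looked for only in notes that the key term has found, the five no-hit wordings are never read. If they are looked for across the whole record, the second rule makes such a chart ineligible while the third assumes capacity is intact. The text needs an edit on either reading.

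**Step 3. What happens for each combination of notes?**

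| Intact-capacity note | Lack-of-capacity note | Key-term hit | Rules that fire |
|---|---|---|---|
| no | no | no | assumed intact |
| no | no | yes (unrelated) | none |
| no | yes | yes | not initially eligible |
| yes | no | yes | initially eligible |
| yes | yes | yes | both |

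D.3 gives no date window and no order of precedence for the last row. If the D.2.d header settles it, any lack-of-capacity note excludes, however old. The study physician's discretion to enroll despite an exclusion covers items 1, 4 and 7 only, so an old, resolved note under item 8 has no stated route to review.

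**Step 4. What do the later safeguards do?**

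- Item 5 bars anyone currently incapacitated, but D.3 names no search for it.
- The diagnosis-code exclusions (for example dementia and serious mental illness) remove some affected Veterans by another route.
- The TICS-m floor of 20 screens cognition, not decision-making capacity.
- The telephone judgment with Care Partner input is optional.
- The practitioner consult is mandatory, but only once someone raises a question, and a chart already classed as intact does not itself raise one.

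None of these specifies another search of the record for documented incapacity.

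**Step 5. Can the effect be sized?** No. The documents do not say how often charts record incapacity or in what words.

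**The case against.** The strongest reply is that the chart step confers initial eligibility only and several layers follow it. A Veteran who is currently incapacitated meets item 5, and one exclusion is enough. D.3 also provides for a brief record review for exclusions not readily found in the data pull, so a reader of the notes may see the entry anyway. The consult before consent is obligatory when a question arises, and nothing limits what the practitioner may look at. All of this stands. A reader might infer that Veterans with documented incapacity would be enrolled, or that the word search is the only protection. The documents support neither inference.

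A reader might also infer that a chart with both kinds of note is eligible and ineligible at once. The D.3 sentences taken literally do say both, but the D.2.d header can be read as making a documented lack of capacity decisive. Nor is a missing look-back an error in itself, since several other exclusions have none. What remains is that precedence is not stated in D.3 and the treatment of an old, resolved note is not addressed.

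Finally, a reader might want a rate. Assuming that 1–3% of charts document incapacity and that 25–50% of those use other wording gives 1,000 × 0.01 × 0.25 = 2.5 to 1,000 × 0.03 × 0.50 = 15 charts per 1,000 passed to mailing and telephone contact. Both inputs are assumptions with no basis in the documents. The result ignores the earlier diagnosis-code exclusions and does not count enrollments, so the point does not rest on it.

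**Conclusion.** The point holds for the initial chart step. Followed as written, D.3 classifies as intact any chart that documents incapacity without the string 'capacity', which contradicts exclusion 8. The later safeguards reduce the consequence but do not correct the classification, because none specifies a return to the record for this purpose. The gap on conflicting notes is real but lesser: it concerns precedence and look-back, not a flat contradiction in eligibility.

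The size of the effect is unknown. The conclusion assumes that staff apply the key-term rule literally; a reviewer who reads more widely would catch some of these charts, but the plan does not require it. No sample size, error rate or outcome comparison is affected. The consequences are for participant protection and for the reproducibility of the eligibility count.

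**What to change.** In D.3:

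1. Replace the single key term with a short list of stems, for example 'capacit', 'competen', 'guardian', 'surrogate' and 'unable to make'. The stem 'capacit' finds capacity, incapacity and incapacitated; 'competen' finds both incompetent and not competent. Together the stems find every wording in the first table.
2. Disregard hits that are not about decision-making, which gives unrelated hits such as lung capacity an outcome.
3. Presume capacity intact only when none of the listed terms is found.
4. Send charts with conflicting entries to the study physician or study RN through the consultation route already in D.3.
5. Reconcile D.3 with exclusion 8 by stating whether an old, resolved note excludes. This is for the investigators to decide. A rule in D.3 that the latest note governs would conflict with exclusion 8 as worded unless both are edited together.

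The cost is a few edited sentences and somewhat more hits to read per chart, within a record review already planned. No extra staff or patients are needed.
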